#### 3.1.1 Primary efficacy outcome data to be collected.

This study is a feasibility study but the data will inform the sample size needed for a future larger randomised controlled trial. In order to calculate the sample size needed for the follow on study, data on treatment accuracy and reproducibility will be collected as part of this feasibility trial. In a previous audit of reproducibility at the Host Institution without any immobilisation (n=30 women) 73.3% of cases had mean systematic errors <3mm and 75% of cases had mean random errors <3mm for central lung depth on treatment verification images. We would expect the S4A bra to either maintain or improve on this reproducibility. However, reproducibility achievements must be viewed in relation to improvements in the dose to organs at risk (mean lung and mean heart dose where applicable). Hence the data from this feasibility trial will be viewed collectively in terms of reproducibility achievements and the ability to reduce the dose to organs at risk.

#### 3.1.2 Primary feasibility outcome

Feasibility of recruitment to main trial: defined as recruitment of 50 participants recruited in a 6month recruitment window at 1 centre.

#### 3.1.3 Secondary efficacy outcomes

This study will evaluate the usefulness of a number of efficacy outcome measures and their suitability for use in the main follow on trial. Efficacy outcomes that we will test in this feasibility trial are as follows:

- Skin reactions using the Radiation Therapy and Oncology Group skin scoring assessment (RTOG)(1) both staff scored and patient self –reported using a new lay reporting skin assessment tool (developed jointly by our patient group and health care practitioner group).
- Dose to organs at risk, including mean ipsilateral lung dose, combined total lung dose, and mean heart dose (for those treated for a left breast cancer).
- Incidence of moist desquamation in the inframammary fold.

- Breast oedema measured via a new self reporting tool (SELF- SizE, Look, Feel, tool).
- Patient comfort measured by a comfort questionnaire developed from interviews with healthy volunteers that have tried the support bra and adaptations of the Kolcaba patient comfort questionnaire for radiotherapy patients(31).
- Patient modesty measured by the patient modesty scale(2) and a newly developed story board of the radiotherapy journey to measure patient experiences of physical exposure.
- Patient empowerment using the 15-item patient empowerment scale for cancer patients(3)
- Participant views on acceptability of the intervention using a specially designed Technology Acceptance questionnaire based on the Technology Acceptance Model(4).
- Therapist views on the intervention using a specially designed Technology Acceptance questionnaire(4).
- Body Image using the 10-item body image scale(5)

## 3.1.4 Secondary feasibility outcomes

- Recruitment and attrition rates (CONSORT data): number of patients assessed for eligibility; reasons for exclusion, numbers discontinuing intervention (with reasons), numbers analysed and excluded from the analysis.
- Number of missing values/incomplete cases: Acceptable rates of missing values for all the questionnaires (see section 5.2) prospectively defined as 0.5% in line with industry standards for phase I-III clinical trials. Unacceptably high error rates will trigger staff retraining and, where refractory, consideration by Trial Steering Committee of exclusion of the instrument from the battery.
- Intervention adherence: Defined objectively as the number of radiotherapy fractions where the bra is used (for the intervention group) divided by the number of fractions prescribed.
- Intervention fidelity: During the study period site observations will be undertaken of treatment set-up for patients in both the control and intervention arms to ensure the support bra is used and positioned correctly and technique protocols are used in a standard manner across intervention and control groups. A checklist of criteria that reflects the protocol for using the support bra will be used to monitor intervention fidelity (see Appendix 4).
- Feasibility of recruiting future participating centres: target sites for the main study will be screened for suitability, by interviewing potential principal investigators.
- Decision on primary endpoint for main trial: descriptive assessment based on the above and sample size estimation

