## 3.1. Success or stop go criteria for this feasibility trial

## Table 1 Stop/Go Criteria for the Feasibility Trial.

Criteria to be assessed and potential outcome	Proposed Action at end of feasibility trial
Random and systematic errors > 3mm for CLD in more than 30% of cases using the bra.	Review bra fit comments across sample and review training and bra use instructions. Further experimental testing (use of healthy volunteers and 3D surface imaging to measure improvements in accuracy and reproducibility, recommended before definitive RCT.
Mean lung dose, no improvement in mean lung doses over control arm.	Review inflation levels used in the study and recommend changes to inflation levels used, further experimental testing recommended before definitive RCT.
Mean heart dose (left sided cases only), no improvement in mean heart doses over control arm.	Review inflation levels used in the study and recommend changes to inflation levels used, further experimental testing recommended before definitive RCT.
Recruitment to sample size (n=50) takes longer than 6-months.	Review recruitment process and devise strategy to enhance recruitment to the definitive RCT.

Retention in study < 80%	Review attrition reasons and identify strategies to remedy ahead of full RCT.
Intervention adherence < 84%	Review comfort questionnaire responses and consider strategies to enhance patient comfort.
RTOG score in the intervention arm ≥3 in one or more cases.	Review of bra fit, inflation levels and dosimetry for affected cases, recommend bra refinement. If a grade 3 (or above) reaction occurs during the course of radiotherapy, treatment will be reviewed by the patient's Oncologist immediately. Treatment may continue without the bra following re-planning at the discretion of the treating Oncologist

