#### 5.2. Number of patients

The sample size for a feasibility study should be adequate to estimate the uncertain critical parameters (SD for continuous outcomes; consent rates, event rates, attrition rates for binary outcomes) needed to inform the design of the full RCT with sufficient precision. A sample size of 40 patients allows a standard deviation, for a continuous outcome such as accuracy of radiotherapy (measured in mm), to be estimated to within a precision of approximately ±23% of its true underlying value with 95% confidence. Therefore, allowing for a 20% attrition or loss to follow-up we propose to recruit and randomise 25 patients per group (50 in total). This SD estimate will be synthesised with standard deviations observed in other published studies and on going trials to provide a robust estimate for use in the sample size calculation for the full trial. Preliminary estimates suggest the definitive RCT would need to have between 192 and 266 patients, in total, to detect a standardised effect sizes of between 0.50 to 0.40 at conventional levels of power (90%) and significance (5% two-sided).

For the parameters such as skin reaction measured by RTOG scoring system, a score of 3 or more on the 0 to 4 integer scale would be regarded as a negative event. With 20 randomised patients in the support bra group; then if none of these patients had a RTOG score of 3 or more; then we would be 95% confident that the true negative event rate would lie between 0 and 16.1%. Observing one or more patients with RTOG scores of 3 or more would suggest that the underlying negative event rate for the support bra, is between 1% and 24%, which is not adequate enough for the support bra in its present form to replace existing practice (ie no immobilisation) and requires further development and refinement.

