## 7.4.3. Assessing patient empowerment

Patients will be asked to complete the 15-item patient empowerment scale for cancer patients (32) at day 0 (Radiotherapy planning CT visit) and once weekly during treatment (ie week 1, week 2 and week 3).

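### The 0.5% limit on missing questionnaire data has no denominator and no rule for withdrawn patients; on either plausible reading it would probably flag most patient questionnaires due after baseline, good ones included

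*Protocol*

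**What the plan says.** Section 3.1.4 of the Protocol introduces the outcome as "Number of missing values/incomplete cases: Acceptable rates of missing values for all the questionnaires (see section 5.2"), and the limit is "prospectively defined as 0.5% in line with industry standards for phase I-III clinical trials". The Trial Summary repeats the 0.5%. The consequence follows in section 3.1.4: "Unacceptably high error rates will trigger staff retraining and, where refractory, consideration by Trial Steering Committee of exclusion of the instrument from the battery".

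Three other places bear on it:

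- Section 5.2 sizes the trial by "allowing for a 20% attrition or loss to follow-up we propose to recruit and randomise 25 patients per group (50 in total").
- Table 1 in section 3.1 calls for action on attrition at "Retention in study < 80" (per cent), so retention of exactly 80% triggers nothing.
- Section 7.4.3 schedules the "15-item patient empowerment scale for cancer patients (32) at day 0 (Radiotherapy planning CT visit) and once weekly during treatment", which gives four time points: day 0 and weeks 1, 2 and 3.

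The limit's cross-reference is to section 5.2. That is the sample-size section, and it lists no questionnaires.

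**The concern.** The rule leaves its unit undefined. Its title joins missing values to incomplete cases, its limit speaks of missing values, and its consequence speaks of error rates. These are three different quantities. A patient who withdraws leaves an incomplete case, and nothing in the rule exempts her. On that reading the trial could meet its own retention criterion and still fail the missing-data limit by a wide margin.

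The stakes are practical. Section 3.1.3 makes testing the outcome measures for the main trial a purpose of this study, and several of the tools are new. A completeness threshold that flags sound and weak instruments alike gives little help in that choice and may set off retraining that nobody needs. This is not detail that can simply wait for an analysis plan: the protocol itself fixes the number in advance and attaches a consequence to it.

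**Working it through.** **Inputs.** Limit 0.5% (section 3.1.4). 40 evaluable patients, 20% attrition, 50 randomised (section 5.2). Empowerment scale: 15 items, 4 time points (section 7.4.3). Body image scale: 10 items (section 3.1.3); its number of time points cannot be read reliably from the assessment matrix, so 1 to 3 are tried. Completion rates below are assumptions, shown as ranges.

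**The plan's own figure.** 40 / (1 − 0.20) = 50, which reproduces. The expected loss at that allowance is 50 × 0.20 = 10 patients. The 0.5% is not derived in the protocol, so there is no calculation behind it to reproduce.

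**Reading A: forms lost to dropout count as missing.**

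- One time point: 0.005 × 50 = 0.25 of a form may be missing, in effect none. One missing form is 1/50 = 2%, four times the limit.
- Empowerment scale overall: 50 × 4 = 200 forms due, and 0.005 × 200 = 1 may be missing. One patient lost after day 0 misses 3/200 = 1.5%. One patient missing only week 3 gives 1/200 = 0.5%, exactly at the limit.
- Ten dropouts after day 0:

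| Forms missed by each | Missing of 200 | Multiple of 0.5% |
|---|---|---|
| 1 | 10 = 5% | 10 |
| 2 | 20 = 10% | 20 |
| 3 | 30 = 15% | 30 |

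- At any single time point after all ten have left: 10/50 = 20%, 40 times the limit.

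Chance of breach over the 200 forms, for an assumed true missing rate p. If forms go missing independently, it is P(X > 1) with X binomial(200, p). If missingness is wholly by patient, one missing patient already gives 4/200 = 2%, so it is 1 − (1 − p)^50.

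| p | Independent forms | Wholly by patient |
|---|---|---|
| 1% | 0.595 | 1 − 0.605 = 0.395 |
| 2% | 0.911 | 1 − 0.364 = 0.636 |
| 5% | 0.9996 | 1 − 0.077 = 0.923 |

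**Reading B: only items on returned forms count.** Attrition plays no part. With 40 completers the empowerment scale has 40 × 4 × 15 = 2400 values, and 0.005 × 2400 = 12 may be missing. The chance of passing is P(X ≤ 12), X binomial(2400, p):

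| True item-missing rate p | Chance of passing |
|---|---|
| 0.25% | 0.991 |
| 0.5% | 0.576 |
| 1% | 0.005 |
| 2% | about 0 |

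For the body image scale with 40 completers and 1, 2 or 3 time points, there are 400, 800 or 1200 values and 2, 4 or 6 may be missing. At a true rate of 1% the chance of passing is 0.237, 0.099 or 0.045.

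**The case against.** The best case for the rule is that Reading B is the intended one. Attrition has its own bullet in section 3.1.4 and its own row in Table 1. The reference to error rates, and staff retraining as the first remedy, suit badly completed forms better than withdrawals. On that reading there is no arithmetical conflict with the 20% allowance, and the denominator could be supplied in an analysis plan. All of this is fair, and it means the conflict with attrition is conditional.

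A reader might also infer that the limit cannot be met at all, that virtually every questionnaire would be marked, or that all instruments would be put up for exclusion. The protocol does not support these:

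- The 20% is a planning allowance and a review trigger, not a forecast, and its timing is not given. Losses after week 3 would leave the day 0 to week 3 forms complete.
- The therapists' questionnaire is not exposed to patient attrition, and baseline forms may be complete.
- The 40-fold excess holds only at a time point after all ten losses, not over the whole empowerment schedule when losses follow day 0.
- Breach triggers retraining. Exclusion is only considered, and only if retraining fails. The limit is not a stop/go criterion in Table 1.
- Instruments are also judged on usefulness, ease of use and agreement with staff scores (section 7.3; Table 2, rows 11 and 12).

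What the objection does not remove is the result under Reading B: settling the denominator in the rule's favour still leaves a limit that an instrument with 99% item completion would usually fail.

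**Conclusion.** The point holds in a limited form. The 0.5% limit lacks a denominator and a rule for withdrawals, and it treats missing data and errors as one quantity. If dropout counts, it contradicts the protocol's own tolerance of 20% attrition, by 10 to 30 times over the empowerment schedule. If dropout does not count, 99% item completion still fails almost always on the empowerment scale (pass probability about 0.005) and in roughly 76% to 95% of cases on the body image scale. Most patient questionnaires due after baseline would therefore probably be flagged, and the rule discriminates poorly between instruments.

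These figures rest on assumed completion rates and, under Reading B, on items going missing independently. Clustering of skipped items within patients would raise the chance of passing at a 1% rate, by an amount the protocol gives no means to estimate. That 0.5% is an industry standard for missing values cannot be checked from the document. The wording suggests a limit meant for data errors, but that is an inference. The rule should be restated; it does not threaten the trial's main conclusions.

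**What to change.** In section 3.1.4 and the Trial Summary, replace the single limit with two criteria:

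- **Form return:** forms received divided by forms due from participants still in the study at each time point. Withdrawals are reported under attrition and retention only.
- **Item missingness:** missing items divided by items due on returned forms.

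Give each a justified level that is compatible with Table 1 and can be judged with 50 patients, where one form at a time point is 2 percentage points. Keep a 0.5% limit only for data errors, if that was its intent, and say so. Tie retraining and Trial Steering Committee review to the new criteria, and correct the cross-reference to section 5.2 so that it leads to the list of questionnaires.

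The cost is a wording amendment and the work of justifying two levels. The stated standard becomes less strict, which should be acknowledged openly.

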#### 4.0 Trial Design

The SuPPORT 4 All (S4A) study is a single centre randomised feasibility trial. The safety of the product in terms of the radiation absorption properties have been fully tested through a series of physics tests performed on both a 6 and 10MV linear accelerators (see Appendix 1). The positional accuracy achievable using the S4A bra has been tested through a Healthy Volunteer Study using 3D surface scanning (stereophotogrammetry). Hence the purpose of this feasibility trial is to test the acceptability of the SuPPORT 4 All bra by patients (in terms of comfort, modesty and usability) and staff (in terms of ease of daily set-up) and to assess the appropriateness of a range of measurement tools that might be used in post implementation surveillance as part of the on-going update to the product technical file.

This study also proposes to assess the impact of the bra on the ability or ease of producing an acceptable radiation treatment plan. To achieve this those patients randomised to the intervention arm will undergo two planning CT scans (using a repeated measures design); one CT scan while

wearing the S4A bra and one scan as normal without the bra. Thus enabling a direct comparison between participants of dose homogeneity achievable with and without the bra.

The following parameters are standard tools or measures that will be adopted in the study (see section 7.0 for more details) some are validated tools others are being tested for the first time in this study:

- Skin reactions using a standard measuring tool Radiation Therapy and Oncology Group skin scoring assessment (RTOG)(1).
- Incidence of moist desquamation in the inframammary fold.
- Dose to organs at risk (mean lung and mean heart doses) taken from the patient's individual dosimetry plan (see section 7 for further details).
- Patient comfort measured via a new comfort questionnaires designed specifically for this study.
- Patient modesty measured by aspects of the patient modesty scale(2) within a newly developed story board of the radiotherapy journey to measure patient experiences.
- Patient empowerment using the 15-item patient empowerment scale for cancer patients(32)
- Technology acceptance from both healthcare practitioners and patients using an adapted Technology Acceptance Tool (based on the Technology Acceptance Model(4)).
- Body Image using the 10-item body image scale(5)

[figure not shown]
In addition, an ancillary patient self-reporting booklet will be used and this contains:

- Sections to record the size of the bra and all the fitting dimensions (strap positions and details about fit) for those in the intervention arm.
- A self-reporting skin scoring scale based on the RTOG system and
- A tool for measuring and monitoring changes in the breast the SELF tool (SizE, Look, Feel).

The self-reporting tools will also be assessed for acceptability and usability in this feasibility study. The purpose of the patient self-reporting booklets is to enhance patient input to their own treatment, provide some opportunity for patient control and for empowerment. To aid this a comparison of patient self-reporting of skin reactions will be assessed against reporting by the healthcare practitioners to measure comparability.

Figure 1. Trial Flow Diagram

## **5.0 Patient Selection and Eligibility**

#### 5.1. Patient selection

Women who have undergone conservative surgery for early breast cancer referred to the Host Institution for post-operative radiotherapy.

#### 5.2. Number of patients

The sample size for a feasibility study should be adequate to estimate the uncertain critical parameters (SD for continuous outcomes; consent rates, event rates, attrition rates for binary outcomes) needed to inform the design of the full RCT with sufficient precision. A sample size of 40 patients allows a standard deviation, for a continuous outcome such as accuracy of radiotherapy (measured in mm), to be estimated to within a precision of approximately ±23% of its true underlying value with 95% confidence. Therefore, allowing for a 20% attrition or loss to follow-up we propose to recruit and randomise 25 patients per group (50 in total). This SD estimate will be synthesised with standard deviations observed in other published studies and on going trials to provide a robust estimate for use in the sample size calculation for the full trial. Preliminary estimates suggest the definitive RCT would need to have between 192 and 266 patients, in total, to detect a standardised effect sizes of between 0.50 to 0.40 at conventional levels of power (90%) and significance (5% two-sided).

For the parameters such as skin reaction measured by RTOG scoring system, a score of 3 or more on the 0 to 4 integer scale would be regarded as a negative event. With 20 randomised patients in the support bra group; then if none of these patients had a RTOG score of 3 or more; then we would be 95% confident that the true negative event rate would lie between 0 and 16.1%. Observing one or more patients with RTOG scores of 3 or more would suggest that the underlying negative event rate for the support bra, is between 1% and 24%, which is not adequate enough for the support bra in its present form to replace existing practice (ie no immobilisation) and requires further development and refinement.

#### 5.3. Inclusion Criteria

All of the following criteria need to be met for inclusion in the study:

- Women
- Age ≥18 years
- Have undergone conservative surgery leaving an intact breast.
- Invasive carcinoma of the breast
- pT1-3, pN0-1, M0 disease
- Referred for whole breast radiotherapy only
- Able to give written informed consent.
- A bra cup size that fits in the S4A bra size 3 and above (ie 28F/30E/32DD/34D/36C and above) see Appendix 1.

All standard systemic therapies are allowed except those prescribed concurrent chemotherapy.

#### **5.4 Exclusion Criteria**

- Previous ipsilateral or contralateral breast cancer (including DCIS).
- Concurrent cytotoxic chemotherapy, (sequential adjuvant chemotherapy is allowed).

- Radiotherapy to regional lymph nodes.
- Requires a radiotherapy boost to the site of the primary tumour bed.

## 6.0 Randomisation

#### 6.1. Randomisation procedure

Prior to randomisation an eligibility checklist should be completed and signed informed consent should be obtained. Allocation will be through block randomisation (with blocks an integer multiple of four); stratified by breast/bra cup size (S4A bra size 3-7 vs. S4A bra size 8-12). The trial statistician will generate a randomisation schedule using existing software. This will be held remotely by the study-co-ordinator (who will not be directly involved in recruiting patients to the study). At the point of randomisation, the recruiting clinician will contact (telephone) the study co-ordinator, give the patient's details and NHS number and receive a study number and treatment allocation in return. At the end of the trial, the complete remote schedule will be checked against the study dataset. Staffing the randomisation line will be straightforward, as randomisation will occur exclusively during office hours.

#### **6.2. Treatment Allocation**

Patients will be randomised 1:1 to receive the intervention (breast radiotherapy with S4A bra one tattoo) or the control (existing radiotherapy set-up with no immobilisation with tattoos).

